present more frequently other mechanisms of AMI (i.e. type 2 myocardial infarctions caused by spontaneous coronary artery dissection, or AMI with non-obstructive coronary artery disease —MINOCA—, i.e. coronary vasospasm or microvascular dysfunction, especially in the younger age group).¹⁵

Most medical treatments that demonstrated clinical benefits in AMI did so mainly in patients with type 1 AMI (antiplatelet drugs, lipid-lowering therapies, beta-blockers...).

Risk factors for atherosclerotic CAD can be classified in four major groups:

- Traditional cardiovascular risk factors. Cardiovascular risk factors are underreported in women who come to the Primary Care consultation.^{16,17} This lack of diagnosis prevents specific preventive actions. Another noteworthy aspect is that while in men there has been a decrease in unhealthy lifestyle habits such as smoking, in women, especially in the younger group, it has remained stable or may even have increased.^{3,18} Obesity and sedentary lifestyle are more frequent in women. Notably, the impact of metabolic risk factors such as diabetes could confer a higher cardiovascular risk in women than in men.¹⁸
 - o Non-modifiable biological risk factors: age, sex, ethnic background, familiar history of cardiovascular disease.
 - o Modifiable risk factors: hypertension, diabetes, dyslipidemia, smoking, obesity.
- Non-traditional risk factors: obstructive sleep apnea syndrome and chronic kidney disease.
- Sex-specific risk factors.^{2,19–25} A number of clinical conditions unique to women that have been identified to be associated with increased risk of cardiovascular disease. Reproductive factors include early menarche, early menopause, history of miscarriages, reproductive treatments, polycystic ovary syndrome (which is closely related to metabolic syndrome and insulin resistance), gestational diabetes, number of pregnancies, breastfeeding and lactation duration, hysterectomy, hormone replacement therapy, use of hormonal contraceptives, history of pre-eclampsia, eclampsia, or pregnancy-associated hypertension ². Female protection against CVD is associated with sex hormone levels as the incidence and severity of CVD increases in postmenopausal

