2. HIPOTHESIS

We have the following three alternative hypotheses.

Compared with men:

- the adherence to secondary prevention strategies after AMI is lower in women, regardless of their baseline differences.
- the control of CV risk factors after AMI is poorer in women.
- The incidence of clinical outcomes and/or use of healthcare resources after AMI is higher in women.

The null hypothesis for each of the previous statements is that there is no difference between men and women for each of the outcomes. The main rationale for our alternative hypotheses is based on gender-related factors rather than on biological differences.

In addition, we hypothesize that there are gender-related factors associated with (non-) adherence to secondary prevention recommendations in women.

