3. OBJECTIVES

General objective. To evaluate if there are differences in the level of adherence to recommended secondary prevention therapies (pharmacological and non-pharmacological) between women and men surviving a type 1 AMI (with obstructive CAD), its potential consequences, and the potential factors related to that difference, if present.

Specific objectives. To compare between women and men:

- 1) The adherence to recommended secondary prevention therapies at 6 months and 12 months measured as the
 - 1a. Proportion of patients adherent to all recommended pharmacological secondary prevention therapies at 6 and 12 months
 - 1b. Proportion of patients adherent to all recommended non-pharmacological secondary prevention therapies at 6 and 12 months
- 2) The relationship of the adherence with control of risk factors, clinical outcomes, and use of healthcare resources
 - 2a. The proportion of patients with optimal control of all cardiovascular risk factors at 6 and 12 months
 - 2b. The incidence of clinical outcomes at 6 and 12 months
 - 2c. The cumulative use of healthcare resources and cost after discharge
- 3) To assess the factors associated with non-adherence to recommended secondary prevention therapies, with special emphasis to socioeconomic factors and gender issues.

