4. STUDY DESIGN AND RESEARCH PLAN

4.1. DESIGN.

Prospective, matched cohort study of patients hospitalized for a type 1 AMI with evidence of obstructive coronary artery disease who are discharged home alive. Women will be enrolled first, ideally in a consecutive manner, as they are the focus of the study. Men will be recruited subsequently as the comparison group, with 1:1 matching for age and ECG presentation. Matching will be performed locally, in each study site (hospital). All patients will undergo 1-year follow-up with clinical and therapeutic adherence evaluation.

Reference cohort: 500 women discharged alive after a hospitalization for a type 1 AMI with significant CAD

Comparator cohort: 500 age (± 2 years) and ECG (STEMI/NSTEMI) locally matched men discharged alive after a hospitalization for a type 1 AMI with significant CAD

4.2. RECRUITMENT.

Participant centers

25 hospitals managing routinely AMIs and representing different regions from Spain will be invited to participate

Patient recruitment

All consecutive women fulfilling all inclusion criteria and without exclusion criteria surviving the index hospitalization will be invited to participate. Subsequently, men with inclusion criteria and without exclusion criteria, matched for age and ECG presentation, will be recruited.

Inclusion criteria

- Hospitalization for a type 1 AMI⁶⁹ (detection of a rise and/or fall of cTn value above the 99th percentile URL and with at least one of the followings: symptoms of acute myocardial ischemia; new ischaemic ECG changes; development of pathological Q waves; imaging evidence of new loss of viable myocardium or new regional wall motion

abnormality in a patterns consistent with an ischaemic aetiology; identification of a coronary thrombus by angiography including intracoronary imaging)

- Presence of obstructive coronary artery disease (CAD)⁷⁰ (i.e. coronary artery stenosis $\geq 50\%$)
- Age > 18 years. No maximal age limit applies
- Signed informed consent

Exclusion criteria

- Terminal disease (expected survival < 12 months)
- Unavailable for 12-month follow-up (i.e.: living abroad, social situation...)
- Does not speak Spanish
- Major active comorbidity (severe renal or liver failure, active cancer requiring chemotherapy...), interfering with regular post-MI management

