5. INITIAL EVALUATION

5.1. BASELINE CHARACTERISTICS

5.1.1. Biological factors

- Anthropological: age, sex, weight, height and body mass index.
- Sex-specific factors of women's cardiovascular risk: menarche age, number of pregnancies, gestational diabetes, early menopause, polycystic ovary syndrome, presence and number of miscarriages, use of hormonal replacement therapy (yes/no, duration), fertility treatments, use of hormonal contraceptives, history of eclampsia or pre-eclampsia, history of breast or endometrial cancer.
- Vital signs: blood pressure (SBP, DBP) and heart rate.
- Risk factors: hypertension, diabetes, hyperlipidemia, LDL, HDL, total cholesterol, triglycerides, lipoprotein(a), uric acid, tobacco and alcohol consumption, chronic alcoholism, HbA1c level, waist circumference, familiar history of premature coronary artery disease or familiar hypercholesterolemia. Pattern of food consumption and practice of physical activity (this will be measured using

questionnaire MEDAS and IPAQ which will be described in the followings sections).

- Comorbidities: prior coronary artery disease (acute or chronic coronary syndrome), prior percutaneous coronary intervention, prior CABG, prior cerebrovascular disease (transient ischemic attack, ischemic stroke), peripheral vascular disease, heart failure, chronic kidney disease, COPD, Obstructive sleep apnea/hypopnea syndrome (OSAHS), atrial fibrillation, autoimmune disorders, anemia, depression (diagnosis of major depressive disorder), anxiety (diagnosis of generalized anxiety disorder) and Charlson Comorbidity Index (CCI).¹⁵

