5.3.3. Pre-defined exploratory outcomes

- Composite outcome of adherence to all secondary CV prevention recommendations 6 months after discharge (all-or-none composite outcome with a binary response)

- Percentage of patients achieving optimal (guidelines-recommended) control of all individual CV risk factors (LDL-cholesterol levels, blood pressure levels, HbA1c levels, smoking, levels of physical activity/sedentary life)
- 12-month incidence of the composite clinical endpoint: All-cause death, all-cause rehospitalization, and all-cause emergency department visits
- Use of healthcare resources at 12 months, including: days hospitalized (re-hospitalizations), number of ED visits, number of cardiac rehabilitation sessions, number of outpatient specialist visits, and number of urgent PCI procedures).
- Assessment of the main predictors of adherence with secondary prevention recommendations in women (biological, disease-related, pharmacological, socio-economic, psychological, gender)
- Composite outcome of adherence to all secondary pharmacological CV prevention recommendations 12 months after discharge, using pharmacy dispensation records.
- In addition, data on changes in dose or drug will be collected to analyze their influence on adherence.
- Evaluation of each individual components of the composite of adherence to secondary CV prevention recommendations 6 and 12 months after discharge (these recommendations will be given to all patients at discharge):
 - Pharmacological therapies
 - Diet
 - Physical activity and
 - Participation in cardiac rehabilitation programs
- Percentage of patients achieving optimal (guidelines-recommended) control of all individual CV risk factors:
 - LDL-cholesterol levels
 - Blood pressure levels
 - HbA1c levels
 - BMI
 - Smoking

- Levels of physical activity/sedentary life
- Diet
- Composite endpoint of cardiovascular death, rehospitalization, and emergency department visits for cardiovascular causes, and urgent coronary revascularization.
- Effect of delays on return to work on adherence to cardiac rehabilitation and other secondary prevention measures.

OUTCOME METRICS

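### As worded, risk-factor control is follow-up status in all patients, so the test of the second hypothesis can mix baseline prevalence with control after the infarction

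*Protocol*

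**What the plan says.** The second hypothesis in Section 2 is that "the control of CV risk factors after AMI is poorer in women". Objective 2a in Section 3 measures this as "The proportion of patients with optimal control of all cardiovascular risk factors at 6 and 12 months".

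Section 5.3.3 gives the outcome as "Percentage of patients achieving optimal (guidelines-recommended) control of all individual CV risk factors" and lists it twice. The first entry names "LDL-cholesterol levels, blood pressure levels, HbA1c levels, smoking, levels of physical activity/sedentary life"; the second adds BMI and diet. Neither entry restricts a component to patients with the factor or refers to the baseline value.

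On comparability, Section 4.1 says "Men will be recruited subsequently as the comparison group, with 1:1 matching for age and ECG presentation", done locally at each site. Section 1 states that "Obesity and sedentary lifestyle are more frequent in women", without figures. Section 5.1.1 collects the baseline state: "Risk factors: hypertension, diabetes, hyperlipidemia, LDL, HDL, total cholesterol, triglycerides, lipoprotein(a), uric acid, tobacco and alcohol consumption", together with HbA1c, BMI, and the diet and activity questionnaires (MEDAS and IPAQ). Section 6 plans multivariable models for sex and each outcome. Covariates are to be chosen by clinical value and by the imbalance seen between the groups.

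**The concern.** The hypothesis concerns what happens after the infarction, and Objective 2 links control to adherence. Never having smoked, or never having had diabetes, cannot result from adherence after discharge, yet both count as success in an all-patient proportion. If a factor is more common in one sex at admission, that sex starts further from the target, and the difference carries into the 12-month contrast even when care and response are identical.

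The distortion can run either way. It can appear to confirm poorer control in women where women start with more of a factor, or hide a real deficit where they start with less. This outcome is the protocol's only measure of one of its three stated hypotheses. The first hypothesis carries an explicit baseline qualifier ("the adherence to secondary prevention strategies after AMI is lower in women, regardless of their baseline differences"); the second does not.

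**Working it through.** **Plan's own figures.** The protocol gives no expected value for risk-factor control. Its only sizing figure is for the adherence composite (42% v 52%, alpha 0.05, power 80%). The two-sided formula gives 390 per group, and 390/4 × (1 + √(1 + 4/(390 × 0.10)))² = 410 with continuity correction, which matches Section 6. It does not bear on this outcome. Allowing for the planned 20% loss, 500 per group leaves 400, which is used below.

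**Model.** Let p be the share with the factor at admission and q the share of those who reach target. Assume that nobody newly acquires the factor. Then the proportion controlled in all patients is 1 − p(1 − q). With the same q in both sexes, the gap is (difference in p) × (1 − q), although true control does not differ. All p and q below are assumptions. The chance of p<0.05 is for a crude two-sided comparison of proportions that ignores the matching.

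**(a) Smoking, identical cessation.** Men p = 0.40.

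| Women p | q | Women | Men | Gap | Chance of p<0.05 |
|---|---|---|---|---|---|
| 0.25 | 0.40 | 85.0% | 76.0% | 9.0 | 90% |
| 0.25 | 0.50 | 87.5% | 80.0% | 7.5 | 82% |
| 0.30 | 0.50 | 85.0% | 80.0% | 5.0 | 46% |
| 0.35 | 0.50 | 82.5% | 80.0% | 2.5 | 15% |
| 0.35 | 0.60 | 86.0% | 84.0% | 2.0 | 12% |

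**(b) Masking.** Smoking in 25% of women and 40% of men, with cessation of 36% and 60%: 1 − 0.25 × 0.64 = 84.0% and 1 − 0.40 × 0.40 = 84.0%. A 24-point deficit in women disappears.

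**(c) False confirmation.** Low activity in 50% of women and 40% of men, with 30% converting in each: 1 − 0.50 × 0.70 = 65% v 1 − 0.40 × 0.70 = 72%, a gap of 7 points (57% chance of p<0.05).

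Among patients with the factor at admission, the difference is 0 in (a), −24 in (b) and 0 in (c), which is correct each time.

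**(d) All-factor composite.** If the remaining factors are jointly met by a share r, independently and equally in both sexes, the smoking gap is multiplied by r. With r of 0.2 to 0.6, women at 25-30%, men at 40% and q = 0.50, the gap is 1.0 to 4.5 points (6% to 25% chance). Opposite imbalances can nearly cancel. Take smoking at 87.5% in women v 80% in men, and obesity in 40% of women v 30% of men with 20% success in each (68% v 76%). The products are 0.875 × 0.68 = 59.5% and 0.80 × 0.76 = 60.8%, a gap of 1.3 points.

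**(e) Would selection on imbalance bring the factor in?** With 500 per group, 40% v 25% gives z = 0.15/√(2 × 0.325 × 0.675/500) = 5.1, so almost certainly. For 40% v 35%, z = 0.05/√(2 × 0.375 × 0.625/500) = 1.6, so it would fail a 5% screen. That threshold is an assumption, since Section 6 gives none. The gap left in that case is the small one in (a), 2 to 3 points.

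**The case against.** The strongest reply is that the protocol states no scoring rule. A reader might infer that it prescribes scoring on follow-up status alone. It does not: it is silent on targets and denominators, and an analysis plan that is not shown may settle them. That stands as to detail. The outcome and Objective 2a are nevertheless both worded as a proportion of patients, whereas the adherence metrics in Section 5.3 are limited to prescribed components, and some drugs to those indicated.

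Second, a reader might infer that nothing deals with baseline differences. Section 6 does plan adjustment for each outcome, the data are collected, and a large imbalance would probably bring the factor in. What remains is that its entry is not fixed and depends partly on the observed data.

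Third, a reader might set the single-factor gaps beside the 10 points used for sizing. That comparison is not supported: the 10 points belong to adherence, and the composite dilutes the gaps or lets them cancel. Nor does Section 1 say that women smoke less. It describes a time trend, falling in men and stable or rising in women. The assumed 25-35% v 40% is illustration only.

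Fourth, attainment in all patients is a legitimate quantity and matches Objective 2a. An analysis restricted to those affected misses newly lost control and compares subsets of different make-up. This is a good reason to keep the all-patient outcome and not to restrict every component. Lipid-lowering therapy is listed for all patients, and diet and activity advice goes to all at discharge.

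**Conclusion.** The point holds in limited form. As worded, absence of a factor before the infarction counts as control, matching does not cover these factors, and adjustment for them is possible but not assured. The contrast meant to test the second hypothesis can therefore reflect prevalence at admission. This matters most for smoking, HbA1c and BMI, less for LDL, and in diluted form for the composite.

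The size cannot be derived from the documents. Under the stated smoking assumptions it is about 2 to 9 points for that component with identical cessation, and 1.0 to 4.5 points in the composite. The direction depends on which sex has more of the factor at admission.

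The priority is moderate. Section 5.3.3 labels the outcome exploratory, although the Summary lists it as secondary. No co-primary outcome and no sample size figure is affected.

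**What to change.** 1. Keep the all-patient proportion as the Objective 2a outcome, and state how patients who do not smoke or have no diabetes are counted.
2. Name the baseline status or level of each factor as a covariate in the adjusted model for that factor, whatever imbalance is observed, including baseline MEDAS for diet and IPAQ for activity. In the composite model, enter the baseline status of its components.
3. For smoking, diabetes/HbA1c, hypertension and BMI, add the proportion controlled among patients who had the factor at the index admission.
4. Keep LDL, diet and activity in all patients, since those recommendations apply to all.
5. Base the conclusion on the second hypothesis on these baseline-conditioned results.

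The cost is wording and analysis code; Section 5.1.1 already collects the data. The downside is smaller denominators. With 400 per group and smoking in 25% of women and 40% of men, 100 women and 160 men remain. At 50% cessation, the 95% interval for the difference is about ±1.96 × √(0.25/100 + 0.25/160) = ±12.5 points.

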However, most comparisons between women and men with AMI are hampered by the major differences in the epidemiology and pathophysiology of AMI,¹³ including the older age of women, their greater comorbidity (particularly, renal disease),¹¹ increased risk of adverse effects with therapies (i.e. bleeding)⁴⁹ and the different proportion of different AMI types (i.e. women presenting more often with type-2 AMI or with non-obstructive coronary artery disease),^{15,55,61} which has therapeutic and prognostic implications. These differences need to be accounted for to improve the accuracy of comparisons and define more clearly the role of sex and gender on the management and outcomes of AMI.⁴⁶

Gender and determinants of adherence to evidence-based therapies after AMI

Age, gender, the presence of comorbidities and polypharmacy are factors that predict adherence to secondary prevention therapies⁶². Women with AMI have been found to have differences in adherence compared with men, with lower adherence to P2Y₁₂ inhibitors (i.e. clopidogrel)⁶³ or a 10% greater probability of non-adherence to statins.⁶⁴ In a study with 148,654 patients with AMI, who had received secondary prevention measures in accordance with the clinical guidelines (loading dose of antiplatelets and chronic doses of aspirin, beta-blockers and ACE inhibitors in patients with AMI and reduced left ventricular ejection fraction, lipid-lowering drugs and medical advice smoking cessation) female gender was associated with poorer adherence on all measures⁶⁵. However, a recent meta-analysis showed a lower adherence to lipid-lowering drugs (OR = 0.87, 95% CI 0.82-0.92) with no differences in the other three major pharmacological groups of secondary prevention (ACE inhibitors/ARA-II, beta-blockers and antiplatelets) in women post-MI,⁶⁶ but the role of the differences in age and comorbidities in these results is unknown. Regarding the adherence to non-pharmacological secondary prevention measures, registries and observational studies have observed that men are less likely to achieve blood pressure goals than women.⁶⁷ The results of the EUROASPIRE V survey also reveal that women change their healthy food habits in compliance with the recommendations, more frequently than men do.⁶⁸

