5.3.1. Co-Primary outcomes

- **Pharmacological primary endpoint:** outcome of adherence to pharmacological therapies (MMAS-8) 12 months after discharge.
- **Non-pharmacological primary endpoint:** Composite outcome of adherence to non-pharmacological secondary CV prevention recommendations 12 months after discharge, including diet, physical activity and participation in cardiac rehabilitation programs.

Adherence will be defined as compliance with at least 80% of each of the CV prevention recommendations separately: medications, cardiac rehabilitation program, diet and physical activity. This outcome is defined as an all-or-nothing endpoint with a binary response. These outcomes are defined as an all-or-none endpoint with a binary response.

5.3.2. Secondary outcomes.

- **Pharmacological primary endpoint:** outcome of adherence to pharmacological therapies (MMAS-8) 6 months after discharge.
- **Non-pharmacological primary endpoint:** Composite outcome of adherence to non-pharmacological secondary CV prevention recommendations 6 months after discharge, including diet, physical activity and participation in cardiac rehabilitation programs.

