- **Primary endpoint:** Composite outcome of adherence to all secondary CV prevention recommendations at 12 months after discharge. The composite is built as an all-or-nothing response to an adherence $\geq 80\%$ in all prescribed components of the endpoint: pharmacological therapies (MMAS-8), diet, physical activity and participation in a cardiac rehabilitation program. Adherence will be defined as having at least 80% compliance with all CV prevention recommendations; drugs, cardiac rehabilitation program, diet and physical activity)
- Measurement of adherence to secondary prevention recommendations: At least 80% of adherence for the following prescribed recommendations at 6 and 12 months:
 - Diet recommendations
 - Physical activity recommendations
 - Drug prescriptions:
 - o Aspirin for all without contraindications
 - o P2Y₁₂ inhibitors for all, according to the time indicated at discharge (if none, use 12 months)
 - o Statins / other lipid-lowering therapies for all
 - o Any of the following if indicated:
 - Beta blockers (if LVEF <0.40 or HF)
 - Angiotensin-converting enzyme inhibitors or angiotensin receptor blockers (if LVEF <0.40 or HF)
 - Glucose control medications (SGLT2 inhibitors/GLP-1 agonists)

1. Measurement of adherence to pharmacological recommendations:

a) The Morinsky Medication Adherence Scale (MMAS-8).⁷⁷ A total score of all items will be calculated with a sum score ranging from 0 to 8 for adherence. MMAS-8 Score will be calculated if the respondent answers at least 6 of 8 items. MMAS is trichomized in three levels of adherence:

- High adherence (score 8)
- Medium adherence (score, 6 to 7)
- Low adherence (score, <6)

b) Records of dispensations in the pharmacy: This is an indirect method to measure compliance based on evaluating the collection of the medication in the pharmacy. Patients who withdrew all medications during the year will be considered adherent. The information will be checked from the medical history that records the withdrawal of drugs from the pharmacy. This will be done for each of the secondary prevention medications to calculate adherence to each of them (aspirin, P2Y₁₂ inhibitors, statins, and beta blockers or ACE inhibitors).

2. Measurement of adherence to non-pharmacological recommendations:

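### The pharmacy-dispensing rule asks for all medications over one year for every drug, which does not match the protocol's own 80% definition of adherence or its drug-specific period for the P2Y12 inhibitor.

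*Protocol*

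**What the plan says.** Section 5.3.1 of the protocol sets the general rule: "Adherence will be defined as compliance with at least 80% of each of the CV prevention recommendations separately: medications", followed by cardiac rehabilitation, diet and physical activity. The outcome metrics repeat it: "At least 80% of adherence for the following prescribed recommendations at 6 and 12 months". Drug prescriptions are in the list that follows, and the P2Y12 inhibitor entry there sets its period "according to the time indicated at discharge (if none, use 12 months".

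Two measures of drug adherence are then described. Item 1.a is the MMAS-8 questionnaire. Item 1.b is pharmacy dispensing: "Patients who withdrew all medications during the year will be considered adherent". The item adds that adherence will be worked out for each drug, naming aspirin, P2Y12 inhibitors, statins, and beta blockers or ACE inhibitors. It gives no per-drug cut-off.

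Section 5.3.3 lists the outcome that uses item 1.b among the exploratory ones: "Composite outcome of adherence to all secondary pharmacological CV prevention recommendations 12 months after discharge, using pharmacy dispensation records". The same section says that "data on changes in dose or drug will be collected to analyze their influence on adherence".

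**The concern.** The protocol fixes one threshold for medication adherence and then gives a measurement rule that does not use it. The rule can also be read in two ways, so two analysts with the same dispensing records could classify the same patient differently. In addition, it applies one year to every drug, while the list above it lets the P2Y12 period vary by patient. A patient whose indicated time is shorter than a year is assessed over different periods in the two places.

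MMAS-8 yields a single total score, so item 1.b is the only method described that gives adherence drug by drug. The choice of reading decides who counts as adherent in those results.

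**Working it through.** **1. Comparison of the texts**

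| Place in the protocol | Threshold | Period |
|---|---|---|
| 5.3.1, definition of adherence | at least 80%, each recommendation separately, medications included | 12 months |
| Outcome metrics, opening list | at least 80%, prescribed recommendations, drugs included | 6 and 12 months; P2Y12 inhibitor by the time indicated at discharge |
| Outcome metrics, item 1.b (dispensing) | *all*; no percentage | one year, every drug |
| Outcome metrics, item e (rehabilitation) | at least 80% of scheduled sessions | – |

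Rehabilitation attendance is also a count of events done over events due, and there the 80% is written out. In item 1.b it is not.

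**2. The two readings of *all***

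- *Every collection of every drug.* The threshold is then 100%, not 80%.
- *Every drug collected.* No share of the supply is specified, so a patient with a few collections of each drug might qualify. The 80% is again not applied.

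**3. Size of the gap under the first reading**

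The protocol gives no dispensing rate, so there is no figure of its own to reproduce on this point. The inputs below are assumptions: 12 monthly collections per drug, each missed independently with probability m. The number of drugs comes from item 1.b, which names four. Beta blockers and ACE inhibitors are conditional on LVEF below 0.40 or heart failure, so three drugs are also shown.

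For k drugs:

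- *All* rule: (1 − m)^(12k).
- 80% rule: 0.80 × 12 = 9.6, so at least 10 of 12 for each drug: P(Bin(12, 1 − m) ≥ 10)^k.

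One drug:

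- m = 2%: 0.98^12 = 0.785; P(≥ 10 of 12) = 0.9985.
- m = 5%: 0.95^12 = 0.540; P(≥ 10 of 12) = 0.9804.

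| m | k | *All* rule | 80% rule |
|---|---|---|---|
| 2% | 4 | 0.98^48 = 37.9% | 0.9985^4 = 99.4% |
| 5% | 4 | 0.95^48 = 8.5% | 0.9804^4 = 92.4% |
| 2% | 3 | 0.98^36 = 48.3% | 0.9985^3 = 99.5% |
| 5% | 3 | 0.95^36 = 15.8% | 0.9804^3 = 94.2% |

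**4. Limits of this calculation**

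- Missed collections are likely to cluster in the same patients. Clustering raises the share meeting the *all* rule and so would tend to narrow the gap. It cannot reverse the order, because anyone who meets *all* also meets 80%.
- The gap depends on frequent collection. With four collections a year, 0.80 × 4 = 3.2, so all four are needed and the two rules coincide by count. With five, 0.80 × 5 = 4, and they separate.

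**5. Reach**

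The pharmacological co-primary outcome (12 months) and its secondary counterpart (6 months) use MMAS-8. The sample size rests on assumed rates of 42% and 52% for the all-or-none composite, whose drug component is also MMAS-8. None of these uses item 1.b.

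**The case against.** The strongest reply is that item 1.b is loosely worded rather than wrong. *All* may mean every drug, in which case the 38% against 99% contrast does not arise. That part stands: 100% collection is one reading and not a stated requirement. It does not remove the mismatch, because the other reading has no collection threshold either.

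It is also fair that 80% is not the working cut-off everywhere. The diet score counts as good at 9 of 14 (64%), physical activity uses IPAQ categories, and MMAS-8 has three levels. But 80% is the stated definition for medications, and dispensing is a measure to which a percentage applies directly.

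Detailed handling rules may well sit in an analysis plan that is not shown. That covers what the protocol leaves open. It does not cover a rule that the protocol states and that conflicts with its own definition.

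Three stronger conclusions might be inferred, and the documents support none of them:

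- *Drugs stopped by a clinician count as non-adherence.* The protocol does not say so. Item 1.b is silent, the 80% list is limited to prescribed recommendations, and changes of dose or drug are collected. A literal reading could produce this result, but that is a gap and not a stated rule.
- *The rule is biased against women.* Section 1 notes that women have "increased risk of adverse effects with therapies (i.e. bleeding", but gives no size and does not link this to stopping drugs. Any figure for such a bias must assume both unequal stop rates and that stops are scored as non-adherence, which is the open point. Size and direction are unknown.
- *Dispensing is the check on MMAS-8.* Section 5.3.3 lists it as one exploratory outcome and gives it no such role.

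**Conclusion.** The point holds in limited form. Item 1.b does not apply the 80% definition that the protocol sets for medications, and its single one-year period conflicts with the P2Y12 entry in the same part of the document. The passages must be reconciled. Item 1.b also leaves unsaid how drugs stopped or switched after discharge are treated.

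If *all* means every collection, the effect on classification is large: about 38% to 9% adherent against 99% to 92% with four drugs, and about 48% to 16% against more than 94% with three. These figures rest on assumed independent monthly collections with 2% to 5% missed; they illustrate the gap and do not predict the trial's results.

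Reach is limited to the exploratory 12-month dispensing composite and the drug-by-drug adherence. No co-primary or secondary result depends on the rule. It is worth correcting because the correction is cheap and would change who is counted as adherent, but it does not threaten the main conclusions.

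**What to change.** Rewrite item 1.b so that it follows the 80% definition:

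- For each drug, dispensing adherence means at least 80% of the supply due (or of days covered) was collected over that drug's own intended period.
- The period ends early at a documented stop or switch, taken from the dose and drug change data already collected under section 5.3.3.
- The composite is met when every drug indicated for the patient meets 80%.
- The period used for the P2Y12 inhibitor in item 1.b and the one in the drug list are made the same.

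This defines how adherence is measured and leaves treatment decisions untouched.

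Cost: a change of wording and some extra analysis. Collection dates or counts would have to be extracted from the pharmacy records in place of a yes/no entry. The protocol does not say whether those records hold usable dates, so this should be confirmed first.
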